#### BACKGROUND:

The goal of the proposed project is the development and evaluation of a novel mobile medical application for the detection and monitoring of strabismus (eye misalignment). The image analysis technology necessary to measure strabismus using the corneal reflection technique (Photographic Hirschberg Test) has been available for many decades (Brodie 1987), however it has never been deployed using a smart phone. A smart phone platform will eliminate barriers of cost (since the hardware is maintained and updated by the smart phone industry), leading to rapid widespread application and allowing the technology to finally reach its potential level of impact for children's' eve care in the detection and management of strabismus. Strabismus causes visual confusion and double vision which ultimately results in the brain suppressing vision from the deviated eye. In children this results in under-development (amblyopia) with permanent vision loss in the deviated eye if not detected and treated at a young age (Rowe, 2012). Strabismus in children is also associated with coordination problems such as postural instability (Lions et. al. 2013) and severe social disadvantages (Lukman et. al. 2011). Strabismus develops in an estimated 3-8% of children in the U.S. (Taylor et.al. 2011; Cotter et.al. 2009; Rowe 2012). The prototype smart phone app (Referred to here as the Mobile Eye Alignment App – MEAA), uses photographic analysis of the corneal reflection (Purkinjie image) generated by the smart phone camera flash. The corneal reflection method uses the displacement of the reflection from the center of the pupil in the deviated eye to calculate the amount of eye misalignment.

This measurement technique will be deployed for the proposed project using the hardware of the Samsung Galaxy, a popular phone with an Android operating system. Preliminary results suggest the app can measure differences in eye alignment of  $1.6^{\circ}$  (2.8 prism diopters). If successfully developed, the app has potential to be utilized to advance pediatric strabismus research by facilitating and reducing the cost of collecting enormous amounts of data from the general population and underserved or remote populations for epidemiologic studies and allowing researchers to capture eye alignment data much more frequently than is currently possible. Such a tool could better delineate the natural history of strabismus and perhaps help determine its causes.

While devices are available which could make these measurements, the costs are prohibitively high (>\$3,000 ea.) and will not reach the widespread availability of smart phones. Clinical goals for the app are to provide eye doctors with an objective measurement tool in the exam room, allow daily monitoring of treatment effects, and eventually to be used as a screening tool by school nurses, pediatricians, and parents. The barriers to market success of stand-alone devices is not the accuracy sensitivity or specificity of photographic analysis technique which has been reported with sensitivity from 53% to near 90% and specificity ranging from 76% to 94% for strabismus detection (Loudon et.al. 2011; Barnard et.al. 2013).

Impact of strabismus screening for the young - Early detection for strabismus in young children, especially during the critical period up to 2 years of age, is important to ensure that treatment is administered as soon as possible (Klaver et. al. 2011; Williams et.al. 2002). The success of amblyopia treatment depends on several factors, but principally on the age of onset and the age at which the treatment is initiated (Taylor et.al. 2011). Therapy for amblyopia is maximally effective if started before age 3 and can be initiated as early as 8 months, underscoring the critical need for early and widespread access to strabismus screening (Epelbaum 1993; Williams et. al. 2002). Indeed, countries with long-standing early vision screening programs have reported significantly reduced rates of amblyopia (Eibschitz-Tsimhoni et.al. 2000). Access to strabismus

screening is also important for older, school age children (age 7-17) suffering from amblyopia, for whom treatment can lead to significant improvements in visual acuity ranging from 20%-70% of patients, depending on their age bracket (Taylor 2011; Scheiman et. al. 2005).

# AIM

## AIM 1:

Develop and test key functionality of the strabismus app by comparing measurements with successive versions of the prototype app to known angles of eye deviation (non-strabismic volunteers will gaze at off axis targets of known eccentricity).

## AIM 2:

Evaluate the strabismus app accuracy and feasibility in a clinical environment. Participants with strabismus will be tested with both the app and clinical methods and analyzed for levels of agreement and test-retest repeatability, satisfaction with the app evaluation, impact on symptoms, and perceived value.

## **OBJECTIVES**:

1) Using simulated strabismus, we will systematically evaluate changes to the prototype app. The app will be tested in various lighting conditions and in participants with various iris colorations, using this information to refine and eventually select the best algorithm.

2) Compare the app measurement with the following common clinical tests of eye alignment: the cover-test with prism neutralization, modified Thorington, or Von Graefe method to determine accuracy, test-retest variability, and robustness of the prototype (optimized in objective 1) to accurately measure strabismus.

3) Determine the best methods for tele-strabismus consultation and rapid delivery of prism treatment, develop a user interface, and determine the perceived value.

## **HYPOTHESES**:

For strabismus ranging from 1 to 30 prism diopters (target range), the optimized version of the app will provide measurements which are not significantly different from the ground truth (simulated strabismus) or clinical tests of eye alignment.

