#### **Ground truth study:**

The subjects will sequentially fixate on the targets of known eccentricity placed on the rear surface of the smartphone along the horizontal direction with their head stabilized in a chin forehead rest (Fig. 3). The app does not need to be used in this manner in actual practice; however, for the purpose of establishing the true deviation values for the fixation targets, such a controlled setup was necessary. The test setup covered an angular range of  $\pm 13$  degree (approximately  $\pm 23D$  with respect to a central fixation corresponding to camera lens).

Figure 3. Experimental setup to measure the accuracy of the app in Study 1. Subjects without strabismus fixated on 13 targets on the rear side of a smartphone placed at a distance of 30 cm with their head resting on a chin–head rest. Twelve of the 13 fixation targets were a black cross on a white background. The center target was the smartphone camera. With the known distances, true eye deviation magnitudes with respect to the central fixation point were computed (angular range covered by the fixation targets was 6138 or 623D) and compared to measurements with the app.

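### The 1 PD lower limit of the hypothesised range is unsupported: the only resolution-type figure is a preliminary 2.8 PD, and no planned analysis examines small deviations on their own

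*Protocol*

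**What the plan says.** **Claim.** The Hypotheses section of the protocol opens "For strabismus ranging from 1 to 30 prism diopters (target range" and continues that "the optimized version of the app will provide measurements" that will agree with the reference. Agreement is defined as "measurements which are not significantly different from the ground truth (simulated strabismus) or clinical tests of eye alignment". No margin, significance level or limit of agreement is attached.

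**Preliminary performance.** The Background says "Preliminary results suggest the app can measure differences in eye alignment of" 1.6 degrees, also given as "2.8 prism diopters". Neither document gives a finer figure.

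**Ground-truth study.** "Subjects without strabismus fixated on 13 targets on the rear side of a smartphone", and "Twelve of the 13 fixation targets were a black cross on a white background"; the remaining one, at the centre, was the camera. The range is 13 degrees to either side, about 23 PD, "with respect to a central fixation corresponding to camera lens". The text does not state the spacing.

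**Analysis.** Secondary outcome 1 measures accuracy by the mean difference from the simulated or measured deviation. Secondary outcome 4 looks at how accuracy varies with age, iris color and refractive error; the size of the deviation is not listed. For Aim 1, the SAP fits one line per subject through all 13 points, taking the slope as the Hirschberg ratio and the intercept as angle kappa. It then regresses app-estimated gaze angle on true angle. Its Bland-Altman analysis covers only the repeatability of the ratio and kappa. For Aim 2, the SAP uses a linear regression of the app against the prism-neutralized cover test. None of these analyses is broken down by size of deviation.

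**The concern.** The hypothesis reaches down to deviations roughly a third the size of the only difference the protocol says the app has measured, without explaining why 1 PD was chosen. That would matter little if the analysis checked the low end, but it does not. A regression over a wide range is determined mainly by its extremes, and an average over all deviations can look good whatever happens at the smallest ones. The study could therefore report agreement from 1 to 30 PD with very little information about 1 to 3 PD. The protocol's clinical goals include screening and daily monitoring, where a validated range starting at 1 PD would be taken at face value.

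**Working it through.** **1. Reproduce the protocol's conversions.** PD = 100 × tan(angle).
- 100 × tan(1.6°) = 2.79 PD; the Background states 2.8.
- 100 × tan(13°) = 23.09 PD; the Ground truth section states about 23.

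Both agree.

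**2. Compare the lower limit with the preliminary figure.** 1 PD = arctan(0.01) = 0.57°. The ratio is 1 / 2.8 = 0.36, so the lower limit is 2.8 times finer.

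**3. Size of the segment.** (2.8 − 1) / (30 − 1) = 1.8 / 29 = 6.2% of the hypothesised range.

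**4. Smallest ground-truth deviation (assumes even spacing).** Thirteen targets make 12 intervals.
- Equal angles: 26° / 12 = 2.17°, and 100 × tan(2.17°) = 3.8 PD.
- Equal distances on the phone: 2 × 23.09 / 12 = 3.85 PD.

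Under either form, no target lies between 0 and about 3.8 PD. Uneven spacing could place one there.

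**5. Weight of the innermost targets in the fitted slope (same assumption).** With targets at −6, …, 0, …, +6 units, the sum of squares is 2 × (1 + 4 + 9 + 16 + 25 + 36) = 182. The two innermost off-centre targets contribute 2, and 2 / 182 = 1.1%. A small constant offset goes into the intercept, which the SAP assigns to kappa.

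**6. How much an overall comparison can hide.** Take an extreme case: an app that always reads zero. Its error at a true deviation d is d, so it stays within 2.8 PD for every d from 1 to 2.8 and exceeds it beyond. The table gives the share of 3,000 simulated studies in which a two-sided 5% t-test of the mean difference detects it. The assumptions, none of them in the documents, are uniformly distributed deviations, normal comparison noise and the values of n. Noise SD is 2.8 PD (treating 2.8 as an SD) or 2.8 / 1.96 = 1.43 PD (treating it as a 95% half-width). The first row also covers zero noise.

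| Deviations | Noise SD | n = 5 | n = 10 |
|---|---|---|---|
| 1 to 30 PD | 0 to 2.8 | 85–90% | 100% |
| 1 to 2.8 PD | 1.43 | 56% | 94% |
| 1 to 2.8 PD | 2.8 | 20% | 48% |

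Over the full range the failure is obvious because of the large deviations. Within the low segment, detection depends heavily on noise and numbers, and the documents give neither.

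**The case against.** Four replies have force.

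**The two figures describe different things.** The 2.8 PD is preliminary and belongs to the prototype; the hypothesis concerns the optimized version and calls 1 to 30 PD a target. A development study may aim beyond its pilot data. The Background also says only that the app can measure differences of this size. It does not call that the smallest measurable difference, an SD or a limit of agreement. A reader might infer that the app cannot distinguish 1 PD from zero, or that the protocol contradicts itself. The text supports neither.

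**A useless app would not pass.** A reader might infer that an app always returning zero would satisfy the plan. It would not: 2.8 PD is nowhere a pass criterion, a constant reading has zero slope against the reference, and the full-range row above shows it being caught. Averaging over subjects can also reveal a bias smaller than a single reading can resolve. What stands is narrower: poor performance confined to the low end could go unnoticed.

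**The low end may not be untested.** A reader might infer that no data exist below 3.8 PD. That depends on the assumed spacing. It also ignores the clinical study, which sets no minimum deviation and includes phoria measurements against the Modified Thorington test with three app readings per subject. Small deviations may well be present; the plan just does not analyse them separately.

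**The larger defect is the missing margin.** A hypothesis of no significant difference without an agreement margin is weak at every angle, and changing the lower limit does not cure that. This is true, but it does not supply the missing support for 1 PD.

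**Conclusion.** The point holds as a gap in support. The hypothesis starts at 1 PD, the only resolution-type figure is 2.8 PD, and no planned analysis isolates the 1 to about 3 PD segment, so larger deviations can carry the conclusion. This much rests on the documents alone.

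Two further statements are conditional. The smallest non-zero ground-truth deviation of about 3.8 PD, and the 1.1% share of slope information, both require evenly spaced targets. The simulated detection rates depend on assumed noise and sample sizes and are illustrative only.

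The affected segment is small, 1.8 of 29 PD (6.2%), and the rest of the range is untouched by this point. It still deserves action, because it determines where the validated range may be said to begin and it can be settled without new measurements.

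**What to change.** Report app-versus-reference agreement, as the mean difference with 95% limits of agreement, separately for deviations below 3 PD (2.8 rounded up), using whatever ground-truth and clinical data exist there. Three details matter:
- Define the stratum by the known angle in the ground-truth study and by the reference test in the clinical study, not by the app reading.
- Keep the two directions of deviation apart, or work with magnitudes, so that errors of opposite sign do not cancel in the mean.
- Allow for repeated readings on the same subject when computing the limits.

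State the target positions and the number of observations in the stratum. State also how narrow the limits must be to count as support; the documents give no such margin, so the sponsor must choose and justify one. Claim 1 to 3 PD only if the stratum meets it. Otherwise, give the validated range as starting at about 3 PD, or at the smallest deviation actually tested.

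The SAP describes itself as written while the data were being published, so this should be labelled a post hoc analysis. For the same reason, adding fixation targets is not proposed: it would probably mean recalling volunteers, and a 1 PD mark would sit only 3 mm from the lens (0.01 × 300 mm).

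The cost is one additional table, a possibly narrower claim, and an estimate that may be imprecise because few observations fall below 3 PD. If there are none, that should be said and the range shortened.

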## **STUDY DESIGN**:

Prospective research and development study

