## **STUDY OUTCOMES**

## Primary outcome:

The primary outcome is a comparison between the app and the ground truth and between the app and clinical tests.

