## Secondary outcome:

1) Accuracy of the app quantified by calculating the mean difference between the app and simulated or measured strabismus.

2) Test-retest repeatability

3) Robustness measure: calculation of the percentage of capture failures (capture failures/ total number of attempted image captures)

4) Analysis of the effect of different factors (i.e. age, iris color, refractive error) on the accuracy.

5) Success rate of tele-strabismus consult and perceived value (captured in a perceived value survey).

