Statistical Analysis Plan

Produced during publication of data

[name], [name], [name], [name], [name]; Development and Preliminary Evaluation of a Smartphone App for Measuring Eye Alignment. *Trans. Vis. Sci. Tech.* 2019;8(1):19.

August 1, 2019

Aim 1: Simulated Strabismus

The Hirschberg ratio (HR) for each subject was determined using data from all 13 fixation points by plotting the app measurement against the known angular deviation for each fixation point, and determining best fit of this scatter plot using linear regression. The slope of this function represents the individual's HR and the *y*-intercept is the individual's angle κ (the angle between the visual and optical axes, represented as κ).^{18,19} We measured the within-subject test–retest repeatability of the app in estimating the HR and κ using a Bland-Altman²⁰ plot to compute 95% confidence interval (CI) of the difference between two trials. Furthermore, we tested the accuracy of using a population average value of the HR by comparing the absolute gaze angles estimated by the app measurements and the true deviation of the fixation targets (via regression analysis using MATLAB; Mathworks, Natick, MA). The HR used for a subject was the average HR of the rest of the subjects.

Aim 2: Strabismus

Linear regression analysis was used to compare the app measurements of strabismus angle with cover test with prism neutralization CTPN measurements. Since the CTPN measurements were done at near fixation to facilitate direct comparison with the app measurements, corrections were made to the recorded CTPN values during data processing to account for the finite distance between the prism and center of rotation of the eye.²² We arrived at a value of the distance between prism and center of rotation of eye by assuming a population average value of 24 mm for axial length²³ and a back vertex distance of 10 mm.

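### The only hypothesis takes non-significance as the standard for the app, while the SAP states no tolerated difference and plans no app-versus-reference limits of agreement

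*Protocol*

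**What the plan says.** The protocol's Hypotheses section contains one statement: for deviations of 1 to 30 PD, the optimized app "will provide measurements which are not significantly different from the ground truth (simulated strabismus) or clinical tests of eye alignment". No other success standard appears in either document.

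The surrounding text points towards estimating agreement, but does not define it:

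- Protocol, Aim 2: participants with strabismus are to be "analyzed for levels of agreement and test-retest repeatability". No method or limit follows.
- Protocol, Primary outcome: "The primary outcome is a comparison between the app and the ground truth and between the app and clinical tests". No metric is named.
- Protocol, Secondary outcome, item 1: "Accuracy of the app quantified by calculating the mean difference between the app and simulated or measured strabismus". No tolerated value and no measure of spread is given.
- SAP, Aim 1: regression is used for "comparing the absolute gaze angles estimated by the app measurements and the true deviation of the fixation targets", with a leave-one-out Hirschberg ratio (HR): "The HR used for a subject was the average HR of the rest of the subjects".
- SAP, Aim 2: linear regression compares the app with the cover test with prism neutralization (CTPN).
- SAP, Aim 1, Bland-Altman: used once, to compare one app trial with another for HR and angle kappa.

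The Study Design section describes a "Prospective research and development study". The SAP's heading says that it was written while the data were being published.

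**The concern.** A measurement comparison should ask how far the new device can be from the reference and whether that distance is acceptable. The hypothesis asks only whether a difference can be detected. The answer depends on sample size and noise as well as on bias, so a small or imprecise study is more likely to support the claim than a large, precise one.

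The Background gives clinical goals of exam-room measurement, daily monitoring and eventual screening. Those uses depend on the error in an individual reading. A mean difference does not describe that error, and the SAP specifies no app-versus-reference analysis that reports it as limits. The promise in Aim 2 to analyse agreement therefore has no matching method, and a reader of the results has no stated basis for saying that the app passed or failed.

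**Working it through.** **Inputs from the documents.** The hypothesis covers 1 to 30 PD. The Background gives a preliminary figure of 1.6 degrees, or 2.8 PD, for differences the app can measure. The Ground truth study uses 13 targets over ±13 degrees, about ±23 PD. Both conversions reproduce: 100 × tan(1.6°) = 2.79 and 100 × tan(13°) = 23.1. The 2.8 PD is used below only as an example bias, because the protocol does not call it a tolerated error.

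**Inputs not in the documents.** Sample size, SD of the app-minus-reference differences, significance level and a difference test are all absent. I assume a two-sided 5% paired t-test, one difference per subject, n = 10 or 20, and SD = 3, 5 or 8 PD.

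**1. Chance that a real bias is non-significant.** The non-centrality is (bias/SD) × √n, referred to a noncentral t with n − 1 degrees of freedom. The critical values are 2.262 (n = 10) and 2.093 (n = 20).

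| n | SD (PD) | Non-centrality | P(non-significant), bias 2.8 PD |
|---|---|---|---|
| 10 | 3 | 2.95 | 25% |
| 10 | 5 | 1.77 | 65% |
| 10 | 8 | 1.11 | 83% |
| 20 | 3 | 4.17 | 2% |
| 20 | 5 | 2.50 | 34% |
| 20 | 8 | 1.57 | 68% |

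The bias is the same in every row. Only precision changes, and the less precise study is the more likely to meet the standard.

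**2. Zero mean bias, large individual error.** With no bias the test is non-significant 95% of the time at any n and any SD. The limits of agreement are bias ± 1.96 × SD, that is ±5.9, ±9.8 and ±15.7 PD at SD 3, 5 and 8. Non-significance does not distinguish these three cases.

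**3. Regression is not a substitute for limits of agreement.** Suppose the app reads 5 PD too high throughout, with SD 3 PD and angles uniform over 1 to 30 PD. The variance of the angles is 29²/12 = 70.1, so r = √(70.1/(70.1 + 9)) = 0.94. The limits of agreement are 5 ± 5.9, or −0.9 to 10.9 PD. The fitted line recovers the bias on average, but a correlation or R² would not show it, and the SAP does not say which regression outputs are judged or against what.

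**4. Why Aim 1 needs more than a mean difference.** Assume symmetric targets over ±23 PD and signed differences. If the app's scale is wrong by 20%, the error at angle x is 0.2x. Errors at +x and −x cancel, so the overall mean difference is 0, while the error at the extremes is 0.2 × 23 = 4.6 PD. Since Aim 1 asks whether an average HR is adequate, a scale error is the main failure to look for.

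**The case against.** The strongest reply is that no wrong test is planned. The hypothesis is one sentence in a development study. The planned work is estimation: agreement in Aim 2, a mean difference as a secondary outcome, and regressions on truth and on CTPN. Those regressions can reveal bias, and they are a fair reading of the comparison named as primary outcome. This stands, and it limits the point to the wording of the hypothesis, the missing criterion and the missing agreement estimate.

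Two stronger readings are tempting, but the documents do not support them. A reader might infer that the study will declare success from a non-significant paired test. Neither document plans such a test, so the percentages above are not operating characteristics of this trial. A reader might also infer that the planned regression would usually let a bias through because the confidence interval of the intercept would often include 0. The SAP states no such rule. Over 1 to 30 PD, that reading also tests an extrapolation to zero angle, where precision is poor, and is the least favourable one available.

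It is also fair to say that an acceptance limit matters less in early development, and that a limit set now cannot be prospective for data already analysed. Neither reply removes the defect in the hypothesis. Limits of agreement can be reported from existing data without any acceptance limit.

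**Conclusion.** The hypothesis is wrong as worded, because non-significance is not agreement and, for any non-zero bias, is reached more easily with less information. The SAP does not repair this: app and reference are compared by regression only, Bland-Altman is used only for test-retest of HR and kappa, and no tolerated difference is stated. The harm lies in the conclusion that the wording permits and in the absent agreement estimate, not in a planned faulty test.

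The actual size cannot be computed, because the documents give no sample size, SD or significance level. In the illustration, a 2.8 PD bias escapes detection from 2% of the time (n = 20, SD 3 PD) to 83% (n = 10, SD 8 PD). The general conclusion does not depend on those choices; the percentages do. The Aim 1 cancellation rests on symmetric targets and signed differences, both assumed.

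**What to change.** Restate the hypothesis as agreement within limits that the sponsor chooses and justifies, and do not cite a non-significant difference as evidence of agreement.

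**Aim 2 (app versus CTPN).** Beside the regression, report the mean app-minus-reference difference with its confidence interval and the Bland-Altman 95% limits of agreement with theirs. Check whether the difference changes with the size of the angle.

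**Aim 1 (simulated deviation, leave-one-out HR).**

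- Judge the slope of app angle on true angle against 1, together with the error at each target or the limits of agreement across the range. Do not rely on the overall signed mean difference alone.
- State whether kappa was removed before reading the intercept as bias.
- Do not compare the individual fits with 1 and 0: there the slope is the subject's HR and the intercept is the subject's kappa.
- Allow for 13 targets per subject with a mixed model or a subject-level bootstrap.

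For data already analysed, label any acceptance limit as post hoc.

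The cost is one reworded sentence, a few SAP lines and a little extra analysis of the same data. The downside is that the result may be inconclusive. With 20 subjects and one difference each, the 95% confidence interval of each limit of agreement has half-width 2.093 × SD × √(1/20 + 1.96²/38), which is about 2.4, 4.1 or 6.5 PD at SD 3, 5 or 8.

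Two neighbouring matters should be handled separately: the Objectives list more clinical reference tests than the SAP's Aim 2 analyses, and the three app readings per subject belong to the Modified Thorington comparison.
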